Allergic Reactions: Cases of allergic reaction/hypersensitivity reactions have been reported.

Severe skin reactions: Stevens-Johnson syndrome (SJS) and toxic epidermal necrolysis (TEN) have been reported. Lenalidomide must be discontinued for angioedema, grade 4 rash, exfoliative or bullous rash, or if SJS or TEN is suspected, and should not be resumed following discontinuation for these reactions. Discontinuation of lenalidomide should be considered if skin rash \geq grade 2 is exfoliative or bullous or if SJS or TEN is suspected. for other forms of skin Lenalidomide should not be resumed following discontinuation for these reactions.

Musculoskeletal and connective tissue disorders: The rare AE of rhabdomyolysis has been observed with lenalidomide. The reports of rhabdomyolysis were confounded by concurrent use of statins and dexamethasone, concurrent viral and bacterial infections, trauma, and serotonin syndrome, which are risk factors for rhabdomyolysis.

Neoplasms benign, malignant and unspecified. Second primary malignancies:

NDMM: In clinical trials of NDMM an increase of invasive SPMs, most notably AML and MDS, has been observed predominantly in subjects receiving lenalidomide in combination with melphalan or immediately following high-dose melphalan and ASCT. The incidence rate was 1.57 per 100 person-years for the combined MPR arms and 0.36 per 100 person-years for the MP+p control arm. Cases of B-cell malignancies were observed in clinical trials where subjects received lenalidomide in

the post-ASCT setting. Patients should be carefully evaluated before and during treatment using standard cancer screening for occurrence of SPMs, and treatment should be instituted as appropriate.

Post-marketing data: Pneumonitis, transient abnormal liver laboratory tests, hyperthyroidism, hypothyroidism, TLS, TFR and allergic conditions including angioedema, SJS and TEN have been identified and are considered by Celgene to be at least possibly related to lenalidomide.

Lactose intolerance: Revlimid capsules contain lactose. Patients with rare hereditary problems of galactose intolerance, the Lapp lactase deficiency or glucose-galactose malabsorption should not take this medicinal product.

Unused capsules: Patients should be advised never to give this medicinal product to another person and to return any unused capsules to their pharmacist at the end of the treatment.

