12.3.1 Starting lenalidomide in renal failure

| Category | Renal Function (Cockcroft-Gault) | Dose in MM |
|---------------------------|---|---|
| Moderate Renal Impairment | CLcr 30-50 mL/min | 10 mg Every 24 hours |
| Severe Renal Impairment | CLcr < 30 mL/min (not requiring dialysis) | 15 mg Every 48 hours |
| End Stage Renal Disease | CLcr < 30 mL/min (requiring dialysis) | 5 mg Once daily. On dialysis days, administer the dose following dialysis. |

If the dose is tolerated, it can be escalated according to local procedures.

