12.3.2 Dose modification guidelines for lenalidomide

The dose modification guidelines as summarized below are recommended to manage both hematological and non-hematological toxicity. Local investigators can decide to not follow this dose modifications if they feel it is not in the best medical interest of the patient.

Hematological toxicity present at start of study should not lead to dose reduction.

| Platelet counts | |
|---|--|
| Thrombocytopenia | |
| When Platelets | Recommended Course |
| Fall to <30,000/mcL | Interrupt lenalidomide treatment, follow CBC weekly |
| Return to \geq 30,000/mcL | Resume lenalidomide at next lower dose. Do not dose below 2.5 mg daily |
| For each subsequent drop <30,000/mcL | Interrupt lenalidomide treatment |
| Return to \geq 30,000/mcL | Resume lenalidomide at next lower dose. Do not dose below 2.5 mg daily |
| Absolute Neutrophil counts (ANC) | |
| Neutropenia | |
| When Neutrophils | Recommended Course |
| Fall to <1000/mcL | Interrupt lenalidomide treatment, follow CBC weekly |
| Return to \geq 1,000/mcL and neutropenia is the only toxicity | Resume lenalidomide at 25 mg daily or initial starting dose |
| Return to \geq 1,000/mcL and if other toxicity | Resume lenalidomide at next lower dose. Do not dose below 2.5 mg daily |
| For each subsequent drop <1,000/mcL | Interrupt lenalidomide treatment |
| Return to \geq 1,000/mcL | Resume lenalidomide at next lower dose. Do not dose below 2.5 mg daily |

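### Two consecutive sentences in section 2.3 make stopping lenalidomide mandatory and then discretionary for the same severe skin reactions, and no operative section settles which applies

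*Protocol*

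**What the plan says.** The paragraph on severe skin reactions in Protocol section 2.3 (Lenalidomide) contains three relevant pieces of text.

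- A mandatory instruction: "Lenalidomide must be discontinued for angioedema, grade 4 rash, exfoliative or bullous rash, or if SJS or TEN is suspected". The same sentence bars restarting the drug afterwards.
- A discretionary instruction in the next sentence: "Discontinuation of lenalidomide should be considered if skin rash" is of at least grade 2 and meets the condition "grade 2 is exfoliative or bullous or if SJS or TEN is suspected".
- A fragment with no action of its own, which runs into a second bar on restarting: "for other forms of skin Lenalidomide should not be resumed following discontinuation for these reactions".

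Section 12.3.2, where a site would look for lenalidomide dose changes, opens with a statement of scope: "The dose modification guidelines as summarized below are recommended to manage both hematological and non-hematological toxicity". The table below it has a platelet block and a neutrophil block. Toxicity of any other kind is mentioned only in a sub-row of the neutropenia rule, "1,000/mcL and if other toxicity", which sets the restart dose after a neutrophil fall. Section 12.3.2 also lets local investigators depart from its guidelines in the patient's interest.

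**The concern.** A patient with an exfoliative or bullous rash of grade 2 or more, or with suspected SJS or TEN, meets both sentences. One removes the decision from the investigator and the other hands it back. This is the only lenalidomide instruction the protocol gives for these reactions, and they can be fatal.

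Patient safety comes first: an investigator who works from the second sentence could in good faith keep a patient on lenalidomide although the first sentence requires a stop. The effect could outlast the four KRd cycles. Section 12.4 continues lenalidomide as maintenance, while both sentences bar restarting once the drug has been discontinued for these reactions. Whether a patient goes on to maintenance could therefore turn on which sentence was followed.

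The second consequence is for reporting. Sections 7 (Investigational plan) and 16.1 name feasibility and safety among the study's purposes. Stops for toxicity belong to that result and should not depend on which of two adjacent sentences a site read.

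**Working it through.** The protocol gives no figure on this point and none needs recomputing. The check is a comparison of triggers, followed by a search for a rule elsewhere that resolves the conflict.

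**Step 1. Set the triggers of the two sentences in section 2.3 side by side.**

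| Trigger | First sentence | Next sentence | Conflict |
|---|---|---|---|
| Suspected SJS or TEN | mandatory stop | stop to be considered | yes |
| Exfoliative or bullous rash, grade 2 or more | mandatory stop (no grade limit) | stop to be considered | yes |
| Exfoliative or bullous rash, below grade 2 | mandatory stop (no grade limit) | not covered | no |
| Grade 4 rash, neither exfoliative nor bullous | mandatory stop | not covered | no |
| Angioedema | mandatory stop | not covered | no |

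**Step 2. Test a two-tier reading.** The pair could be consistent if the second sentence dealt with milder events than the first. It does not. The first sentence sets no grade threshold for exfoliative or bullous rash, so a rash of grade 2 or more lies inside it. Suspected SJS or TEN is named in both without any qualifier. Every trigger of the discretionary sentence is thus already in the mandatory one. Read literally, the pair is even inverted: an exfoliative rash below grade 2 meets only the mandatory rule, while the same rash at grade 2 or above also meets the discretionary one.

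**Step 3. Look for a rule that settles it.**

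- Section 12.3.2: its stated scope includes non-haematological toxicity, but its rows are platelets and neutrophils. The other-toxicity sub-row applies only on recovery from neutropenia. It names no skin reaction and contains no stopping rule.
- Section 12.2.3: this is a non-haematological table, but for carfilzomib. Its general row for toxicity of grade 3 or more acts when the event is attributed to carfilzomib.
- The opening paragraph of the Safety chapter: investigators must follow the dose-reduction and adjustment guidelines in every patient. It does not say which skin-reaction sentence is the guideline.
- Section 12.4: it gives the maintenance dosing and says nothing on skin reactions.

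No section gives one of the two sentences precedence.

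**Step 4. Ask whether the conflict could come from text extraction.** The fragment on other forms of skin may have lost words when the PDF was read, so nothing is built on it. The two sentences before it are each complete and contradict each other without it.

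**Step 5. Frequency.** The only rash figure in section 2.3 is 10.2% with lenalidomide and dexamethasone, for rash in general. In 50 treated patients that would be 0.102 × 50 = 5.1, about 5 with a rash of any kind. The exfoliative, bullous or suspected SJS/TEN subset must be smaller, and the protocol gives no rate for it.

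**The case against.** The strongest reply is that one course of action meets both sentences. A site that stops lenalidomide satisfies the mandatory wording and the discretionary wording together, while a site that continues breaches an explicit requirement. This stands as a reading of the words, and it means a site that continued could not claim full compliance. It does not remove the conflict, because a reader of the second sentence is told that the decision is open.

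It can also be said that section 2.3 is drug background, that it already carries lenalidomide instructions for hepatic and thromboembolic events, and that 12.3.2 is only a recommendation from which investigators may depart. All of that is correct, so having the rule outside 12.3.2 is not in itself a fault. But the skin text is worded as an instruction and nothing in the treatment chapter replaces it. Latitude to depart from a guideline also presupposes that one guideline exists.

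Four stronger readings are tempting and are not supported.

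- A reader might infer that the second sentence directs continued full-dose lenalidomide. It does not: it prescribes no dose, and the Safety chapter leaves interruptions for other reasons to the physician.
- A reader might extend the conflict to every severe skin reaction listed. Three of the five rows in the comparison are not contradicted.
- Because 12.3.1 is headed "Starting lenalidomide in renal failure", a reader might infer that a patient whose renal function falls on study has no lenalidomide rule and stays on 25 mg rather than 10 mg, a ratio of 25/10 = 2.5. Section 12.3 sets 25 mg except where renal function is reduced and does not limit that exception to entry. The renal row for carfilzomib in 12.2.3 is triggered by change from baseline, so it is no parallel. No 2.5-fold discrepancy is established.
- A reader might take all 50 patients and their 21 × 4 = 84 scheduled lenalidomide doses as the size of the problem. That is planned exposure to the drug, not the number who would meet the conflict.

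**Conclusion.** The contradiction is real and narrow. For two triggers, exfoliative or bullous rash of grade 2 or more and suspected SJS or TEN, adjacent sentences of section 2.3 give a mandatory and a discretionary stopping instruction. Neither 12.3.2 nor 12.2.3 resolves it, and 12.3.2 does not contain the non-haematological rules that it says it contains.

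The number of patients affected is unknown and probably small. No effect on the primary estimate is shown: the primary analysis is on the mITT population with worst-case imputation of missing dichotomous outcomes (16.5, 16.7), and the safety analysis is descriptive (16.6). The weight of the point lies in the seriousness of the reactions and in this being the protocol's only lenalidomide instruction for them. That makes it more than a clerical slip, and it should be corrected.

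The conclusion rests on the literal wording of two complete sentences. It assumes that no other trial document available to sites settles the matter. It takes no view on which instruction is clinically right.

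**What to change.** The sponsor's clinicians should:

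1. Reconcile the two sentences in section 2.3 so that each trigger has exactly one instruction, and decide what that instruction is.
2. Complete or delete the fragment on other forms of skin.
3. Carry the resulting rule into 12.3.2, or cross-reference it there, so that the section matches its stated scope. If 12.3.2 is meant to cover blood counts only, its opening sentence should say so and point to section 2.3 for the rest.
4. State whether the investigator's freedom to depart from 12.3.2 extends to this rule.

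The cost is a wording amendment to sections 2.3 and 12.3.2 and notice of it to sites. No visits, tests, patients or analyses are added.

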2.4 Dexamethasone – potential adverse events

Allergic Reactions: Anaphylactoid reaction, anaphylaxis, angioedema.

Cardiovascular: Bradycardia, cardiac arrest, cardiac arrhythmias, cardiac enlargement, circulatory collapse, congestive heart failure, fat embolism, hypertension, hypertrophic cardiomyopathy in premature infants, myocardial rupture following

recent myocardial infarction, edema, pulmonary edema, syncope, tachycardia, thromboembolism, thrombophlebitis, vasculitis.

Dermatologic: Acne, allergic dermatitis, dry scaly skin, ecchymoses and petechiae, erythema, impaired wound healing, increased sweating, rash, striae, suppression of reactions to skin tests, thin fragile skin, thinning scalp hair, urticaria.

Endocrine: Decreased carbohydrate and glucose tolerance, development of cushingoid state, hyperglycemia, glycosuria, hirsutism, hypertrichosis, increased requirements for insulin or oral hypoglycemic agents in diabetes, manifestations of latent diabetes mellitus, menstrual irregularities, secondary adrenocortical and pituitary unresponsiveness (particularly in times of stress, as in trauma, surgery, or illness), suppression of growth in pediatric patients.

Fluid and Electrolyte Disturbances: Congestive heart failure in susceptible patients, fluid retention, hypokalemic alkalosis, potassium loss, sodium retention.

Gastrointestinal: Abdominal distention, elevation in serum liver enzyme levels (usually reversible upon discontinuation), hepatomegaly, increased appetite, nausea, pancreatitis, peptic ulcer with possible perforation and hemorrhage, perforation of the small and large bowel (particularly in patients with inflammatory bowel disease), ulcerative esophagitis.

Metabolic: Negative nitrogen balance due to protein catabolism.

Musculoskeletal: Aseptic necrosis of femoral and humeral heads, loss of muscle mass, muscle weakness, osteoporosis, pathologic fracture of long bones, steroid myopathy, tendon rupture, vertebral compression fractures.

Neurological/Psychiatric: Convulsions, depression, emotional instability, euphoria, headache, increased intracranial pressure with papilledema (pseudotumor cerebri) usually after treatment, insomnia, mood swings, neuritis, neuropathy, paresthesia, personality changes, psychic disorders, vertigo.

Ophthalmic: Exophthalmos, glaucoma, increased intraocular pressure, posterior subcapsular cataracts.

Other: Abnormal fat deposits, decreased resistance to infection, hiccups, increased or decreased motility and number of spermatozoa, malaise, moon face, weight gain.

Dexamethasone: It may not be excluded that the efficacy of oral contraceptives may be reduced during dexamethasone treatment. Effective measures to avoid pregnancy must be taken.

2. ¹⁸F-FDG PET/CT

¹⁸F-FDG PET/CT is a sensitive functional imaging modality. The updated International Myeloma Working Group (IMWG) criteria consider patients with focal skeletal lesions and increased uptake with underlying osteolytic destruction in one of the new imaging modalities as indicative of active myeloma (16, 17). In the last years, the significance of ¹⁸F-FDG PET and PET/CT in evaluation of MM has increased. PET/CT is considered a modality of high sensitivity in detecting both medullary and extramedullary disease, while its ability in treatment response assessment and its prognostic value have been documented (18-23). Although its routine application in the follow-up of MM is not yet recommended, ¹⁸F-FDG PET/CT appears to be useful in the monitoring of MM and has been proposed to strengthen the evaluation of the quality of treatment response (17, 19, 20, 24-26).

3. RESEARCH HYPOTHESIS

KRd consolidation will demonstrate high efficacy in NDMM patients after standard first line treatment and can convert the patients that are PET-CT positive in to negativity. Elimination of PET-CT-positivity will be a supplement to elimination of MRD measured by Euroflow.

4. STUDY RATIONALE

PET-CT positivity after first line treatment is a prognostic marker for outcome. At ASH2015, [name] presented data showing that PET-CT is an OS prognostic marker, that it is better than MRI, and that the best time to evaluate on this marker is pre-maintenance (Moreau et al, ASH 2015, Abstract 395). Between thirty and forty percent of the total of patients in these data were PET-positive after 8xRVD or 5xRVD+HDM-ASCT, although the complete data set is not yet available. This is probably marginally higher in the VTD/VCD+transplant population.. The following questions are as of today unanswered:

- a) Can KRd consolidation eliminate PET-CT-positivity in these patients? In what proportion of patients?
- b) How will elimination of PET-CT-positivity correspond to elimination of MRD measured by Euroflow?

In Europe, the most common induction regimes before autologous transplant is VTD and VCD. VRD will probably also be used increasingly in the coming years.. Even though other first-line regimes are in studies, financial matters will keep all mentioned regimes in use for an undetermined period, longer in some countries than in others. The choice of KRd is made on the basis that it will take time before K is a standard of care in first line, and even then, it will probably compete with other regimes. In the relative short term, most patients will not have received KRd in first line. Adding to that is the ASPIRE data where KRd is a standard-of-care treatment in next relapse.

There is an ongoing study of KRd vs R maintenance after ASCT (NCT02659293), where patients can be included disregarding their response status after transplant. In the present study proposal with a non-randomized study design, the focus is on the subgroup with PET-CT-positivity as this is increasingly being used as a measure of minimal residual disease complementary to phenotypic and molecular MRD assessment.

5. STUDY OBJECTIVES

6.1 Primary objective

To assess the proportion of patients that are PET-positive after standard first line treatment (transplant eligible patients), and how many of these can become PET-negative after four cycles of KRd consolidation.

6.2 Secondary objectives

The correspondence between PET-CT results and MRD dynamics by intra-patient comparison. Evaluating safety, quality of life and efficacy of KRd consolidation in this population.

6. ETHICAL AND REGULATORY CONSIDERATIONS

The study will be conducted in accordance with the ethical principles of the Declaration of Helsinki, the ICH-GCP Guidelines, the EU Clinical Trial Directive (2001/20/EG), the Directive (2005/20/EG) and applicable regulatory requirements. The local investigator is responsible for the proper conduct of the study at the study site. National Ethic Committees and National Medicines Agencies in Norway,

Denmark and Sweden will approve the study protocol and any substantial amendment. In accordance with the Declaration of Helsinki, patients have the right to withdraw from the protocol at any time for any reason. The investigator also has the right to withdraw patients from the protocol in the event of intercurrent illness, adverse events and treatment failure after a prescribed procedure, protocol violations, cure, administrative reasons or other reasons. If a patient decides to withdraw from the protocol, all efforts will be made to complete and report the observations as thoroughly as possible. A complete final evaluation at the time of the patient's withdrawal should be made together with a statement of the reason to withdraw.

The clinical trial sponsor-investigator is the physical person or legal entity that is interested in the performance of the trial, signs requests for authorization addressed to the Regional Ethics Committee (REK) and regulatory authority of Norway and is responsible for the trial, including its performance, initiation and completion. The sponsor-investigator will be responsible for ensuring compliance with applicable legal guidelines. Investigators must agree with this protocol and know in detail the properties of the drug used in this clinical trial. Investigators must provide the patient with a patient information sheet and help him/her to understand the explanation provided. It is important to tell the patient that his/her participation in the study is voluntary and that it will not affect patient-physician relationship. In addition, it will be guaranteed that all people involved in the study will observe the confidentiality of any information related to the patient. All participants in the study are covered by national insurance systems for patients in clinical studies.

Each patient is assigned a unique patient study number at registration. In study documents, the patient's identity is coded by a patient study number. The local investigator will keep a subject enrolment and identification log that contains the code key, the personal identification data linked to each patient study number. This data is filed at the investigational site and should only be accessed by the investigator and the supporting site staff or by representatives of the sponsor-investigator or a regulatory agency, and only for monitoring visits, audits and inspections. The Information and Consent Form also explains that for data verification purposes, an authorized regulatory authority, an ethics review board or a monitor performing quality control

may require direct access to parts of the hospital or practice records relevant to the study including patients' medical history.

7.1 Informed consent

Written informed consent of patient is required before any study related procedure. The investigator should provide enough time for patient to discuss about all details of the study. All questions concerning the study will be answered to the satisfaction of the patient before possible obtaining of consent. The content of the patient information letter, informed consent form and any other written information provided to patients will be in compliance with ICH-GCP and other applicable regulations and should be approved by the Ethics Committee before use. Whenever new important information relevant to the patient's consent will be available, the patient information letter, informed consent and any other written information will be revised. Any revised informed consent form and written information should be approved by the Ethics Committee before use. The patient should be informed in a timely manner if new information becomes available that might be relevant to the patient's willingness to continue participation in the study.

